### **5.7.2.1.5** Pregnancy

A serum pregnancy test will be performed for female subjects at the time points presented in the Schedule of Events (Section 10.1). If a subject becomes pregnant while on the study, this should be reported immediately to the investigator, the subject will be withdrawn from the study and the medical monitor and the subject will be instructed to follow-up with his or her personal physician. All pregnancies are to be reported as an AE and followed for outcome.

## 5.7.2.2 Clinical Laboratory Tests

Clinical laboratory and diagnostic screening tests will be performed at the time points presented in the Schedule of Events (Section 10.1) and will be collected in accordance with acceptable laboratory procedures. Clinical laboratory testing will be performed by Spaulding Clinical Laboratory, West Bend, Wisconsin, and Laboratory Corporation of America (LabCorp), Dublin, Ohio. The clinical laboratory tests that will be performed are presented in Table 5-1. Unused clinical laboratory test samples will not be stored for future use.

Clinical laboratory results will be reviewed by the investigator or designee together with data in the eCRF. Any values outside the reference range will be evaluated for clinical significance. If a value is determined to be clinically significant, the subject will be instructed to follow-up with his or her personal physician. The investigator or designee may repeat the clinical laboratory tests if deemed appropriate. The investigator will maintain a copy of the laboratory accreditation and the reference ranges for the laboratory used.

 Table 5-1
 Clinical Laboratory and Diagnostic Screening Tests

Hematology	Serum Chemist	ry	Urinalysis
Complete blood count	Albumin		Appearance
Hematocrit	Alkaline phosph	atase	Bilirubin
Hemoglobin	Alanine aminotr	ansferase	Color
Platelet count	Aspartate amino		Glucose
Red blood cell count	Bicarbonate		Ketones
White blood cell count	Blood urea nitro	gen	Leukocyte esterase
(with automated differential)	Calcium		Microscopic examination: red
,	Chloride		blood cells; white blood cells;
	Direct bilirubin		epithelial cells; bacteria, crystals,
	Glucose		casts, etc. (if present)
	Lactic dehydrog	enase	Nitrite
	Magnesium		Occult blood
	Phosphorus		pH
	Potassium		Protein
	Serum creatinine	e	Specific gravity
	Sodium		Urobilinogen
	Total bilirubin		
	Total protein		
	Uric acid		
Diagnostic Screening Tests:			
Serum		Urine	
Hepatitis panel (hepatitis B surfa	ce antigen and	Drug screen inc	luding: amphetamines, barbiturates,
hepatitis C virus antibody) and h			s, cannabinoids, cocaine, ethanol,
immunodeficiency virus antibody			clidine, propoxyphene, and
antigen/antibody combination tes		methadone	
Serum human chorionic gonadot			
test for all female subjects	L L 2 J		

## 5.7.2.3 Vital Sign Measurements

Vital signs (blood pressure, heart rate, respiratory rate, and oral body temperature) will be measured using an automated device at the time points presented in the Schedule of Events (Section 10.1). The subject should be in a supine position, if possible, for a minimum of 5 minutes before vital signs are measured.

# 5.7.2.4 Safety 12-Lead Electrocardiograms

Safety 12-lead ECGs will be performed at the time points presented in the Schedule of Events (Section 10.1). The subject should be in a supine position, if possible, for approximately 10 minutes before safety 12-lead ECGs are measured. The safety 12-lead ECGs will be reviewed by the investigator at the study clinic to detect any immediate safety concerns.

## 5.7.2.5 Physical Examinations

Physical examinations will be performed at the time points presented in the Schedule of Events (Section 10.1).

The complete physical examination at Screening will include, but not be limited to, assessments of the head, eyes, ears, nose, throat, skin, thyroid, nervous system, respiratory system, cardiovascular system, abdomen (liver and spleen), lymph nodes, and extremities. Height, weight (without shoes and wearing the lightest possible clothing), and calculation of body mass index (kg/m²) will be performed at Screening only.

During the study, skin at the sites of topical application of the study drug will be examined for signs of irritation during the treatment period, upon discharge (or early termination), and at the follow-up visits. At the follow-up visits, a symptom-directed brief physical examination may be performed at the investigator's discretion

If an abnormality is observed upon physical examination, the subject will be instructed to follow up with his or her personal physician.

## 5.7.3 Demographics and Medical History

Demographic data (date of birth, gender, race, and ethnicity) will be collected at Screening.

Each subject will provide a complete medical history at Screening that will be reviewed at Check-in. Specific information relating to any prior or existing medical conditions/surgical procedures will be recorded in the subject's eCRF.

# **5.8.** Study Treatments

### **5.8.1** Treatments Administered

#### Part 1

- La Roche Posay (Cream), Anthelios SX Daily Moisturizer Cream, Face Sunscreen SPF 15 with Mexoryl SX
- Hawaiian Tropic (Lotion); Island Sport Ultra-Light High Performance Sunscreen, SPF 50
- Neutrogena (Spray), Ultra Sheer Body Mist SPF 45
- Banana Boat (Spray); Sport Performance Coolzone Continuous Spray Sunscreen, SPF 50

Approximately 2 mg of sunscreen formulation per 1 cm^2 of body surface will be applied topically 4 times per day for 4 days to approximately 75% of the body surface area.

#### Part 2

- Hawaiian Tropic (Lotion); Island Sport Ultra-Light High Performance Sunscreen, SPF
   50
- Neutrogena (Aerosol Spray), Ultra Sheer Body Mist SPF 100
- Supergoop (Non-Aerosol Spray), Sunscreen Mist with Vitamin C SPF 50
- Supergoop (Pump Spray), Sun Defying Sunscreen Oil with Meadowfoam SPF 50

Approximately 2 mg of sunscreen formulation per 1 cm^2 of body surface will be applied topically once on Day 1 and 4 times per day on Days 2-4 to approximately 75% of the body surface area.

The antecubital areas will be avoided when applying the sunscreen due to potential contamination of the sites used for IV PK blood sample collection.

## 5.8.2 Method Assigning Subjects to Treatment

### 5.8.2.1 Randomization Process

### Part 1 and Part 2

The FDA project biostatistician will create the specifications that will be used to generate the randomization schedule. The specifications will be based on the protocol requirements and appropriate statistical programming with consideration for study design, number of treatments, number of subjects planned for enrollment, stratification, and blocking.

Based on these specifications, the project biostatistician (or designee) will generate a dummy randomization schedule. The schedule is generated by a SAS®/R or other program, which produces output file(s) and/or SAS or R dataset(s).

The project biostatistician (or designee) distributes the 'dummy' randomization schedule to specified personnel for review. Any change (e.g., change in block size, change in stratification levels) that requires an update to the specifications will reset this process. Minor changes (e.g., display formatting) will not require a change to the specifications.

No transfer is necessary if the unblinded randomization biostatistician also created the 'dummy' randomization.

The randomization biostatistician is responsible for generating the final randomization schedule.

Randomization will occur after informed consent is obtained, either after completion of check-in procedures on Day 0 or just before dosing on Day 1. Unique subject numbers will be used in sequential order based on each subject's order of qualification.

In both Part 1 and Part 2 of the study, subjects will be randomly assigned to 1 of 4 different treatments, thus each subject will receive one of the sunscreen formulations by the end of the study. For subjects in Part 1: 1) La Roche Posay (Cream), Anthelios SX Daily Moisturizer Cream, Face Sunscreen SPF 15 with Mexoryl SX; 2) Hawaiian Tropic (Lotion); Island Sport Ultra-Light High Performance Sunscreen, SPF 50; 3) Neutrogena (Spray) Ultra Sheer Body Mist SPF 45; or 4) Banana Boat (Spray); Sport Performance Coolzone Continuous Spray Sunscreen, SPF 50. For subjects in Part 2: 1) Hawaiian Tropic (Lotion); Island Sport Ultra-Light High Performance Sunscreen, SPF 50; 2) Neutrogena (Aerosol Spray), Ultra Sheer Body Mist SPF 100; 3) Supergoop (Non-Aerosol Spray), Sunscreen Mist with Vitamin C SPF 50; or 4) Supergoop (Pump Spray), Sun Defying Sunscreen Oil with Meadowfoam SPF 50.

Replacement subjects (if needed) will be assigned to the treatment group of the subject they are replacing.

The treatment groups are presented in Table 5-2.

**Table 5-2** Treatment Groups

Study Part	Subjects (n)	Treatment Group	Treatment
1	6	A	La Roche Posay (Cream), Anthelios SX Daily Moisturizer Cream, Face Sunscreen SPF 15 with Mexoryl SX
1	6	В	Hawaiian Tropic (Lotion); Island Sport Ultra- Light High Performance Sunscreen, SPF 50
1	6	С	Neutrogena (Spray) Ultra Sheer Body Mist SPF 45
1	6	D	Banana Boat (Spray); Sport Performance Coolzone Continuous Spray Sunscreen, SPF 50
2	12	Е	Hawaiian Tropic (Lotion); Island Sport Ultra- Light High Performance Sunscreen, SPF 50
2	12	F	Neutrogena (Aerosol Spray), Ultra Sheer Body Mist SPF 100
2	12	G	Supergoop (Non-Aerosol Spray), Sunscreen Mist with Vitamin C SPF 50
2	12	Н	Supergoop (Pump Spray), Sun Defying Sunscreen Oil with Meadowfoam SPF 50

All randomization information will be secured and housed in a locked storage area, accessible only by the randomization personnel and the assigned pharmacist and his or her verifier.

# 5.8.3 Identity of Study Drug

The topical sunscreen formulations described in Section 5.8.1 are commercially available OTC products containing the active components avobenzone, oxybenzone, octocrylene, ecamsule, homosalate, octisalate and octinoxate, where applicable.

## 5.8.4 Management of Clinical Supplies

## 5.8.4.1 Study Drug Packaging and Storage

The topical sunscreen formulations will be obtained from commercial sources and stored according to the manufacturer's directions.

## 5.8.4.2 Study Drug Accountability

Good clinical documentation practices will be employed to record the receipt, storage conditions, accountability, and use or return of the study drug. The study drug will be stored in a secure location with access to the study personnel who will be managing the storage, dispensing, and accountability of the study drug.

Upon completion or termination of the study, final accountability review by the study monitor, and written authorization from the sponsor, all unused and/or partially used study drug should be returned or destroyed at the study clinic. It is the investigator's responsibility to ensure that the sponsor has provided written authorization for study drug disposal, the disposal process follows the study clinic's standard operating procedures, and appropriate records of the disposal are documented and maintained. No unused study drug may be disposed until fully accounted for by the study monitor (or designee). Documentation of unused study drug should include subject number, medication identity (medication #, period #), date, and quantity of study drug used.

# 5.8.5 Blinding

Both parts of this study are open-label; therefore, blinding is not applicable.

# 5.8.6 Treatment Compliance

At Screening, as part of the eligibility assessment, it will be confirmed that subjects can comply with the protocol-defined procedure of topical study drug application. All applications of the study drug will be administered in the study clinic either under direct observation of or administered by clinic personnel, and recorded in the eCRF.

### 5.8.7 Prior and Concomitant Medications

Subjects are prohibited from having received or applied the topical sunscreen formulations used in the current study within 7 days before Check-in (Day 0). Subjects are also prohibited from having used any personal care product(s) containing any active

sunscreen ingredient, such sunscreen products, hand or body moisturizing lotion, makeup or foundation, lip balm, or lipstick, within 7 days before Check-in (Day 0).

Subjects will be instructed not to take any medications, including OTC products, without first consulting with the investigator.

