Safety evaluations will include adverse event (AE) monitoring, vital sign measurements, and physical examinations. All AEs reported by the subject or observed by the investigator or clinical research unit (CRU) staff will be recorded. Any AE reported after the informed consent is signed and before study drug application will be recorded as medical history.

Subjects will remain in the CRU after admission on Day 0 until the morning of Day 7 following completion of scheduled End-of-Study activities for part 1. For part 2, subjects will undergo the same

	schedule but will return to the clinic for follow-up visits on Days 10, 14 and 21. Subjects will then be discharged following completion of End-of-Study activities.
	Subjects are not allowed to use products containing any of these active ingredients from 7 days before check-in until completion of End-of-Study procedures.
Inclusion Criteria:	Subjects who meet all of the following inclusion criteria will be eligible to participate in the study:
	1. Subject signs an IRB-approved written informed consent and privacy language as per national regulations (e.g., Health Insurance Portability and Accountability Act authorization) before any study-related procedures are performed.
	2. Subject is a healthy man or woman, 18 to 60 years of age, inclusive, who has a body mass index of 18.5 to 29.9 kg/m², inclusive, at Screening.
	3. Subject has normal medical history findings, clinical laboratory results, vital sign measurements, 12-lead electrocardiogram (ECG) results, and physical examination findings at Screening or, if abnormal, the abnormality is not considered clinically significant (as determined and documented by the investigator or designee).
	4. Subject must have a negative test result for alcohol and drugs of abuse at screening and Check-in (Day 0).
	5. Subject has no known or suspected allergies or sensitivities to any components of the sunscreen formulation.

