#### 5.1.4 Common Procedures

Details of study visits and study procedures are described in Section 5.6 and Section 5.7, respectively, and the overall Schedule of Events for both parts of the study is presented in Section 10.1.

In both parts of the study, approximately 2 mg of sunscreen per 1 cm² of body surface (calculation per method of Dubois) will be evenly applied 4 times per study day (except for a one-time application on the first day in part 2) to areas of the body typically exposed to the sun: face, ears, neck, torso, arms, and legs (approximately 75% of the body surface area). The antecubital areas will be avoided when applying the sunscreen due to potential contamination of the sites used for intravenous (IV) PK blood sample collection. The topical applications of the study drug will be administered with subjects in swim wear to simulate real world settings as well as for easy application. In addition to swim wear, subjects may wear scrubs in between applications and at other times throughout the day/night. Subjects are required to shower each morning after the first PK blood sample collection (and before the first sunscreen application for that day), but not at other times during the day. And, subjects should not use any personal care products which contain avobenzone, oxybenzone, ecamsule, octocrylene, homosalate, octisalate or octinoxate during the study.

Blood samples (approximately 10 mL per sample) will be collected for determination of avobenzone, oxybenzone, octocrylene, ecamsule, homosalate, octisalate and octinoxate (where applicable) plasma concentrations.

Safety evaluations will include adverse event (AE) monitoring, vital sign measurements, and physical examinations. All AEs reported by the subject or observed by the investigator or CRU staff will be recorded. Any AE reported after the informed consent is signed and before study drug application will be recorded as medical history.

Subjects will remain in the CRU after admission on Day 0 until discharge on the morning of Day 7. In Part 2, subjects will return to the clinic on Day 10, 14 and 21 for follow-up PK sampling (Days 10, 14 and 21) and tape stripping (Days 14).

Subjects are not allowed to use products containing any of the active ingredients from 7 days before check-in until completion of End-of-Study procedures.

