### 5.6.3.1 Check-in

The following procedures and assessments will be performed at Check-in (Day 0) as outlined in Appendix A: Schedule of Events:

- Review inclusion/exclusion criteria to confirm subject eligibility
- Perform drug and alcohol screening (amphetamines, barbiturates, benzodiazepines, cannabinoids, cocaine, alcohol, opiates, phencyclidine, propoxyphene, and methadone)
- Perform a serum pregnancy test (female subjects only)
- Perform Fitzpatrick skin type assessment
- Admit subject to the study clinic
- Randomization (after completion of check-in procedures on Day 0 or just before dosing on Day 1)
- Record concomitant medications
- Monitor for AEs

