# 5.6.5 Follow-up

The following procedures and assessments will be performed on Days 10, 14 and 21 for Part 2:

- Measure vital signs (blood pressure, heart rate, respiratory rate, and oral body temperature)
- Collect PK blood samples (10 mL) after dosing as follows:
  - o Day 10: 216 hours after first dose on Day 1 (Part 2 only)
  - o Day 14: 312 hours after first dose on Day 1 (Part 2 only)
  - o Day 21: 480 hours after first dose on Day 1 (Part 2 only)
- Physical examination of skin at the sites of topical application for signs of irritation
- Symptom-directed brief physical examination at the investigator's discretion

- Record concomitant medications
- Monitor for AEs

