All data will be presented in data listings. Data from subjects excluded from an analysis population will be presented in the data listings but not included in the calculation of summary statistics. The number of subjects who enroll in the study and the number and percentage of subjects who complete each assessment will be presented. The frequency and percentage of subjects who withdraw or discontinue from the study and the reason for withdrawal or discontinuation will be summarized. Continuous demographic and baseline characteristic variables (age, height, weight, body mass index) will be summarized overall and by treatment using descriptive statistics (number of subjects, mean, standard deviation [SD], median, interquartile range [IQR], and minimum and maximum). The number and percentage of subjects in each class of categorical demographic and baseline characteristic variables will also be summarized.

5 Pharmacokinetic (PK) Analyses and Primary/Secondary Outcomes

The PK sampling schedule for this study is summarized in Appendix A. The following PK parameters will be determined for each subject in Part 1 and Part 2:

Across all study days

- Maximum concentration (observed peak drug concentration) (C_{\max})

Day 1

- Maximum concentration (observed peak drug concentration) (C_{\max})
- Time at which C_{\max} occurs (T_{\max})
- AUC from time 0 to the 23 hour time point (C_{last}) (AUC_{0-23})

Days 2 and 3

- Residual drug concentration (predose level) (C_{trough})
- Concentration 3 hours after the last dose of the day

Day 4

- Maximum concentration (observed peak drug concentration) (C_{\max})
- Time at which C_{\max} occurs (T_{\max})
- Elimination rate constant (K_{el}) and terminal half-life ($t_{1/2}$); calculated after final dose using all the available data up to last study sample (144 hours for Part 1; 432 hours for Part 2)
- AUC from time 71 to the 95 hour time point (AUC_{73-95})
- AUC from time 0 extrapolated to infinity ($AUC_{0-\text{inf}}$) and/or last observed time point

Day 5, 6, 7, 10 (Part 2 only), 14 (Part 2 only) and 21 (Part 2 only)

- Residual drug concentration (C_{trough})

The primary and secondary outcomes of this study are as follows:

Primary Outcome:

1. Maximum* Avobenzone concentration (C_{\max})

Secondary Outcomes:

1. Maximum* Oxybenzone concentration (C_{\max})
2. Maximum* Octocrylene concentration (C_{\max})
3. Maximum* Ecamsule concentration (C_{\max})
4. Maximum* Homosalate concentration (C_{\max})

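### Use of other sunscreen-containing products is banned to End-of-Study but not asked about on Days 10, 14 and 21, so undetected home use in Part 2 could lengthen the half-life and raise late residual concentrations

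*Protocol*

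**What the plan says.** **The ban.** Protocol 5.8.7 gives only an entry window: "Subjects are prohibited from having received or applied the topical sunscreen formulations used in the current study within 7 days before Check-in (Day 0". It sets the same window for personal-care products with an active sunscreen ingredient, as do exclusions 11 and 12. Section 5.1.4 goes further: "Subjects are not allowed to use products containing any of the active ingredients from 7 days before check-in until completion of End-of-Study procedures". The synopsis says the same. Section 5.1.4 adds that "subjects should not use any personal care products which contain avobenzone, oxybenzone, ecamsule, octocrylene, homosalate, octisalate or octinoxate during the study".

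**The check.** The eligibility criteria are reviewed at Screening (5.6.2) and on Day 0 (5.6.3.1: "Review inclusion/exclusion criteria to confirm subject eligibility"). The Part 2 visits on Days 10, 14 and 21 (5.6.5) list vital signs, PK blood, skin examination, adverse events and "Record concomitant medications". Neither that list nor Table 10-1 has a product-use item. Section 5.8.7 also states: "Subjects will be instructed not to take any medications, including OTC products, without first consulting with the investigator".

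**The analysis.** SAP section 5 has Kel and half-life "calculated after final dose using all the available data up to last study sample", which it puts at 432 hours for Part 2. SAP Attachment A has the last sample at 480 hours. Protocol 5.7.1.4 accepts Kel only with at least 3 points and a coefficient of regression of at least 0.98. It withholds half-life and AUC0-inf otherwise, and also when extrapolation exceeds 20%. The SAP repeats neither rule. Neither document says how to treat samples taken after use of a banned product.

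**The concern.** The entry window shows that the authors regard outside products, including makeup, lip balm and moisturizer, as a source of the assayed ingredients. The same source is open again for 14 days once Part 2 subjects go home, and nothing in the visit schedule asks about it.

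The Day 10, 14 and 21 samples are the only PK data beyond 144 h and carry the information on how long the ingredients persist. Pharmacokinetics is part of the Part 2 primary objective. Late concentrations are low, so a small added amount is a large proportional change, and on the log scale it looks like slow elimination. If the question is not asked during the study, affected samples cannot be identified afterwards.

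**Working it through.** **1. Sampling window.** Nominal hour = (Day - 1) x 24. Day 10 gives 216, Day 14 gives 312 and Day 21 gives 480, as scheduled. The SAP's 432 h does not reproduce: 432/24 + 1 = Day 19, when no sample is taken. Counting from the first Day 4 application, 480 - 72 = 408; from the last, 480 - 78 = 402.

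**2. Model for half-life.** The documents give no half-life, late concentration or assay limit, so these are assumptions: C(t) = 4 x 2^(-(t - 95)/T) ng/mL, samples at 95, 120, 144, 216, 312 and 480 h, and a constant amount *a* added at the three outpatient samples. Fit ln C on t by least squares; fitted half-life = ln 2 / (-slope).

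Worked case, T = 72 h, *a* = 0.5:
- Clean values: 4.000, 3.144, 2.496, 1.248, 0.495, 0.098.
- With the addition: 4.000, 3.144, 2.496, 1.748, 0.995, 0.598.
- Logs: 1.386, 1.146, 0.915, 0.558, -0.005, -0.514.
- Mean t = 227.83; Sxx = 107,113; Sxy = -520.9.
- Slope = -520.9/107,113 = -0.004863; half-life = 0.6931/0.004863 = 142.5 h.

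| True T (h) | *a* (ng/mL) | Fitted (h) | Change | r | r-squared | 0.98 rule read as r |
|---|---|---|---|---|---|---|
| 30 | 0.1 | 71.9 | +140% | 0.917 | 0.842 | rejected |
| 48 | 0.1 | 74.1 | +54% | 0.980 | 0.961 | borderline pass |
| 48 | 0.5 | 134.0 | +179% | 0.940 | 0.883 | rejected |
| 72 | 0.1 | 88.4 | +23% | 0.997 | 0.995 | passes |
| 72 | 0.5 | 142.5 | +98% | 0.983 | 0.967 | passes |
| 120 | 0.1 | 132.6 | +11% | 0.9998 | 0.9997 | passes |
| 120 | 0.5 | 186.9 | +56% | 0.9975 | 0.995 | passes |

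Read as r-squared, the rule also rejects 48 h with 0.1 and 72 h with 0.5.

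**3. Leverage.** The 480 h sample has leverage 1/6 + (480 - 227.83)^2/107,113 = 0.76, so it largely sets the slope.

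**4. If 432 h is taken literally** (480 h sample dropped, additions at 216 and 312 h only): 48 h with 0.1 gives 56.4 h (r = 0.999), 72 h with 0.1 gives 79.4 h, 72 h with 0.5 gives 112.6 h (r = 0.994), and 120 h with 0.5 gives 177.3 h (r = 0.994). The bias shrinks but remains.

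**5. If the fit starts at 81 h** (all samples after the last application at 78 h): 72 h gives 86.1 h with 0.1 and 129.8 h (r = 0.982) with 0.5; 120 h with 0.5 gives 179.1 h. The picture is the same.

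**6. The 20% extrapolation rule.** Extrapolated area = Clast/Kel. For 72 h with 0.5 it is 0.598/0.004863 = 123 ng·h/mL, against 567 from 95 to 480 h by the logarithmic trapezoidal rule: 123/(123 + 567) = 17.8% at most, so it passes. For 120 h with 0.5 it is 252 against 774, or 24.5%. That case is reported only if the area before 95 h adds about 232 ng·h/mL or more.

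**7. Residual concentrations.** These are summarised whatever the fit. At T = 72 h the clean Day 21 value of 0.098 becomes 0.198 with *a* = 0.1 and 0.598 with *a* = 0.5, about 2 and 6 times too high.

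**8. Plausibility of *a*.** With an assumed body surface of 1.6-2.0 m2, 2 mg/cm2 x 75% x 4 applications = 96-120 g/day. At T = 72 h the model level at the last application is 4 x 2^(17/72) = 4.71 ng/mL, so 0.1 is 2.1% of it and 0.5 is 10.6%. If exposure is proportional to amount and strengths are equal, these correspond to about 2-2.5 and 10-13 g/day. The larger value would need a body product; lip or face products alone are unlikely to reach it.

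**The case against.** - **The ban already covers the whole study.** A reader of 5.8.7 alone might infer that the restriction lapses after entry. The synopsis and 5.1.4 contradict that. What is missing is verification, and 5.8.7 does not repeat the on-study ban.
- **Use may be captured anyway.** Concomitant medications are recorded at all three visits, OTC products need prior consultation, and the protocol treats sunscreens as drugs and lists cosmetics under 5.8.7. Capture of an OTC sunscreen is plausible. The visit items do not ask about makeup, lip balm or moisturizer, and the consultation rule is worded for medications.
- **The 0.98 rule is a safeguard.** This largely stands for isolated contamination. If only the 480 h sample were raised by 0.1 ng/mL, a true 48 h would fit as 71.5 h, but r = 0.955 and nothing would be reported. The same holds for 30 h with 0.1 (r = 0.81), 48 h with 0.5 (r = 0.76) and 72 h with 0.5 (r = 0.89); 72 h with 0.1 passes (86.9 h, r = 0.991). So the largest distortions cannot be read as what the trial would report. Repeated use keeps the line straighter and can pass. Where the rule rejects, half-life and AUC0-inf are lost with no recorded cause.
- **The main outcomes are Cmax.** This stands. Cmax would change only if home use exceeded the treatment-period peak.
- **Tape strips.** Home use should not affect the Day 7 strip if it is taken before discharge. The Day 14 strip is exposed only if a product reaches the lower back.

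**Conclusion.** The concern holds as a gap in verification and data handling; the restriction itself runs to End-of-Study. Undetected home use on Days 7-21 would bias half-life and the Day 10, 14 and 21 residual concentrations upward, and the plan could neither detect nor examine it. The Day 14 skin residue could be affected; Cmax is unlikely to be.

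The size depends on assumptions the documents cannot settle: mono-exponential decline, 4 ng/mL at 95 h, and 0.1-0.5 ng/mL added at all three outpatient samples. For true half-lives of 72-120 h, fits that pass the 0.98 rule read as r are too long by about 11% to 98%, though the 120 h case with 0.5 ng/mL may instead be withheld by the 20% rule. At shorter half-lives the rule mostly rejects the fit. Nothing in the documents shows that such use will occur or how often, so these figures illustrate vulnerability and are not a prediction. The change is worth making because it is cheap and the information cannot be recovered later.

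**What to change.** 1. In protocol 5.6.5 and Table 10-1, add an eCRF item at Days 10, 14 and 21: use since the last visit of any sunscreen or personal-care product containing a study active, with product and date.
2. In 5.8.7, cross-refer to the on-study ban in 5.1.4.
3. In SAP section 5, flag PK samples and Day 14 tape strips taken after reported use, by analyte where the product's contents are known. Prespecify the Kel, half-life, residual-concentration and tape-strip summaries with and without flagged data. Deleting every later sample after any reported use would go too far, since it would discard analytes that the product does not contain.
4. Reconcile the SAP's 432 h with the 480 h last sample, and state whether the protocol's 0.98 rule applies and whether it means r or r-squared.

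Cost: one question at three existing visits, a cross-reference and a short SAP paragraph. The item relies on self-report, so concealed use would remain, and the sensitivity summaries would rest on somewhat fewer late samples.
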